Insurance companies do not ordinarily identify their members with AF who might be appropriate candidates for OACs, and they perform no standard outreach to either clinicians or members regarding treatment of AF. Individuals who are identified for this trial will have had their health care providers bill under the diagnosis code of AF at least twice, with at least one billed diagnosis within the last 12 months. Thus, this trial involves no new identification of AF, since the method of ascertainment is through billing by providers based on their diagnosing AF. The current standard of care is for clinicians and their patients with AF to decide together whether anticoagulation for the diagnosed atrial fibrillation is appropriate. All Data Partners collaborating in the IMPACT-AFib trial are insurers (or affiliates of insurers), not care providers, and the clinicians are not employees of the Data Partners.

There is no current evidence that the communications by insurers (like those being assessed in this trial) will have any effect on use of anticoagulation. All eligible patients included in the trial who do not appear to fill an OAC prescription will receive an intervention, as they will either be in the early intervention or the delayed intervention cohort.

XI. INSTITUTIONAL REVIEW BOARD/INDEPENDENT ETHICS COMMITTEE

Before study initiation, the co-principal investigators must have written and dated approval/favorable opinion from the IRB/IEC for the protocol, and any other written information to be provided to prospective participants.

The investigators should provide the IRB/IEC with reports, updates, and other information (e.g., expedited safety reports, amendments, and administrative letters) according to regulatory requirements or institution procedures.

XII. INFORMED CONSENT

Consent will be waived. The reasons for the waiver include:

- 1. The contacting of the delayed intervention patients for consent would be an intervention by itself and might affect the results of the trial.
- 2. The intervention is entirely consistent with a quality improvement initiative that the health plans could initiate on their own. Thus, the intervention is very low risk for harm.
- 3. The intervention only adds on to the existing care of and programs for patients. There are no restrictions placed on the delayed intervention group, as a result of the trial.
- 4. It would be impractical to collect informed consent on the patients included in this trial.

The waiver of informed consent is consistent with the approach that has been taken in several similar clinical trials, the first using individual patient randomization, the others cluster randomized:

- 1. UH3 Pragmatic Trial of Population-based Programs to Prevent Suicide Attempt (NCT02326883)
- 2. The HMO Research Network CERT: A randomized trial of direct-to-patient communication to enhance adherence to beta-blocker therapy following myocardial infarction (NCT00211172)
- 3. MI FREE: A Randomized Evaluation of First-dollar Coverage for Post-MI Secondary Prevention Therapies (NCT00566774)
- 4. STOPCRC: Strategies and Opportunities to Stop Colon Cancer in Priority Populations (NCT01742065)

XIII. INDEPENDENT ADVISORY COMMITTEE

An independent advisory committee (IAC), consisting of members independent from the study team and with expertise in statistics, anticoagulation for atrial fibrillation, engagement, health plan management, and/or in practical clinical trials, will serve to enhance patient safety and trial integrity. The IAC will meet with study leadership at least twice. The first meeting will occur before intervention materials are mailed, and the second will take place two months after all mailings are sent. In addition, other meetings will occur if deemed necessary by the IAC chair, study leads and/or the FDA. The study team will provide the IAC with the study protocol before any intervention materials are mailed and will brief the IAC on any issues (or lack thereof) that have been raised 2 months after the last mailing has occurred. The IAC will advise on concerns that arise. An IAC charter describes the roles, responsibilities, and operations of the IAC.

XIV. STATISTICAL CONSIDERATIONS

A. SAMPLE SIZE AND POWER CALCULATIONS

Our target sample size is 80,000 patients. All enrolled patients and/or their providers will be targeted by mailing (early or delayed) provided they are eligible at time of mailing and able to be contacted.

1. Primary Endpoint

The following assumptions were used to determine the sample size and power for the primary endpoint assessing the proportion of AF patients with evidence of at least one OAC prescription fill through the date on which at least 80% of eligible study participants have at least 12 months of follow-up time:

- 33% OAC initiation rate in the delayed intervention arm over the first year of the study
 - In a Sentinel feasibility assessment of identified health plan members meeting similar inclusion and exclusion criteria as this trial, 33% had evidence of OAC initiation in a 1 year period of follow-up.
- 38% OAC initiation rate in the early intervention arm (a 5% absolute improvement in OAC initiation over the 33% OA initiation expected in the delayed intervention arm over 1-year follow-up)
- 1-year attrition rate: 30% dropout or lost-to-follow-up
- Two-sided type I error of 0.05
- Roughly 10,000 patients (Table below) will yield more than 99% power to detect a 5% absolute difference

[figure not shown]

Power	Total sample size (2-arm)	Early Intervention	Delayed Intervention
90%	5610	2805	2805
95%	6910	3455	3455
99%	9718	4859	4859

Total Number of Patients in a 2-arm study (Unadjusted for dropouts)

OAC Initiation Endpoint (33% Control Rate), continuity corrected Chi-square

2. Important Secondary Analysis of Stroke or TIA

A study with approximately 80,000 patients is well powered for the outcome of stroke or TIA over the course of the follow-up through the date on which at least 80% of eligible study participants have at least 12 months of follow-up time, under certain assumptions listed below:

- 1-year stroke or TIA rate: 18% among patients not treated with OAC
- 1-year stroke or TIA rate: 7% among patients treated with at least 1 OAC fill
- Duration of follow-up: 1 year
- 33% of delayed intervention patients will have at least 1 fill of OAC, meaning the 1 year stroke or TIA rate in the delayed intervention group would be 14.4%
- If 38% of early intervention patients have at least 1 fill of OAC (meaning the 1 year stroke or TIA rate in the early intervention group would be 13.82%, i.e., an absolute reduction of 0.55%), the study will have 46% power to detect this 0.55% reduction. However, if 40.5% of early intervention patients have at least 1 fill of OAC (meaning the 1 year stroke or TIA rate in the early intervention group would be 13.54%, i.e., an absolute reduction of 0.83%), the study will have 80% power to detect this 0.83% reduction.

- 1-year attrition rate: 30% dropout or lost-to-follow-up
- Two-sided type I error of 0.05
- The sample size has 80% power to detect a 0.5% absolute reduction in stroke, assuming a cumulative 1-year incidence of stroke of 4.2% in control (delayed intervention arm) patients and 3.7% in intervention (early intervention arm) patients. The assumption is that patients not on oral anticoagulation have an annual stroke rate of 5%, and stroke will be reduced by 50% (HR=0.5) in the treated (anticoagulated) population. The 80% power requires that 52% of early intervention arm patients are treated at 1-year as compared to 33% in the control arm.

B. POPULATIONS FOR ANALYSIS

All analyses will be based on a modified intention-to-treat principle (i.e., all identified early intervention patients who meet eligibility and are mailed the intervention will be included; using "pseudo" wave assignments, all identified delayed intervention patients who meet eligibility at the time of corresponding early mailings will be included in the analysis). The primary endpoint will be calculated based on the proportion of patients with evidence of at least one OAC prescription fill over the course of the follow-up through the date on which at least 80% of eligible study participants have at least 12 months of follow-up time. An as-randomized analysis will be performed for the primary endpoint as a sensitivity analysis. All possible person-time will be used to assess participants' outcomes; patients will have different duration of follow-up and that will be accounted for in the analyses. Patients will be censored from the analysis at the time of death, disenrollment from the health plan, loss of medical or pharmacy coverage, or change in eligibility for inclusion in research based on health plan membership. The statistical analysis plan (SAP) provided more information and outlines in detail how granular aggregate data will be received from each Data Partner in lieu of patient-level data.

XV. OUTCOME DEFINITIONS

All outcome definitions will be based on available claims data.

- 1. Evidence of OAC start: the proportion of AF patients who have at least 4 INR values measured or who fill at least one OAC prescription for apixaban, dabigatran, edoxaban, rivaroxaban, or warfarin over the course of the follow-up through the date on which at least 80% of eligible study participants have at least 12 months of follow-up time
- 2. Time to OAC start: the time to first OAC initiation, as defined by the first fill date for apixaban, dabigatran, edoxaban, rivaroxaban, or warfarin. If there was no prescription fill for these medications, but the patient had 4 or more INR values measured over the study period, the date of the first INR measurement will be used for initiation of OAC.
- 3. OAC prescription coverage: the proportion of days that AF patients have OAC prescription fills over the duration of the study. The assumption is that a 30-day or 90-day supply will last for the planned period, even in the case of warfarin, when the length of time that a prescription lasts may be less well defined. Patients will only be included in this secondary analysis, if they had a prescription fill for apixaban, dabigatran, edoxaban, rivaroxaban, or warfarin.
- 4. OAC rates at follow-up: proportion of patients with an active oral anticoagulant dispensing at the end of the one-year follow-up. This will include patients with apixaban, dabigatran, edoxaban, rivaroxaban, or warfarin medication fills that encompass the end of the study period. If there was no prescription fill for these medications, this will also include patients with 4 or

more INR values measured over the study period, who had an INR value measured within 60 days of the end of the approximately one-year follow-up.

- 5. Rate of stroke or TIA: the incident rate of stroke or TIA related hospitalizations; stroke, excluding transient ischemic attacks (TIAs), will also be assessed
- 6. Rate of bleeding related hospitalization: the incident rate of hospitalizations for any bleeding
- 7. Health care utilization: the total counts of health care utilization (number of outpatient visits, emergency department visits, hospital admissions, etc.) for AF patients, including AF and non-AF related care
- 8. In-patient all-cause mortality: patients with in-hospital death
- 9. All-cause mortality: in a subset of patients with mortality status

XVI. STATISTICAL ANALYSES

A. DEMOGRAPHICS AND BASELINE CHARACTERISTICS

Baseline characteristics of eligible early and delayed intervention cohorts will be based on the claims data at the time of randomization. Frequency distribution and summary statistics for demographic and baseline variables will be presented by early intervention group, delayed intervention group, and for the overall study population. Key demographic and baseline variables to be summarized include: geographic region, age, sex, risk factors for stroke, risk factors for bleeding, and select comorbid conditions. Continuous variables will be summarized as mean (±SD) and median (25th, 75th percentiles); the comparison between the two groups will be conducted using Wilcoxon rank-sum test. For the continuous variables in combined study population, the mean will be summarized. Categorical variables will be presented as counts (percentages) and will be compared between groups by using Pearson's chisquare or Fisher's exact test, as appropriate.

B. RESPONSES FROM PROVIDERS

As part of the provider intervention materials, providers will have the opportunity to respond to the patient's health plan and give an explanation for why their patients were not being treated with OAC via a postage paid postcard. The data collected from these responses will be aggregated by rationale for non-treatment and reported as counts (percentages) by the coordinating center. Data will not be linked to specific patients or providers.

C. EFFECTIVENESS ANALYSES

The proportion of patients with evidence of at least one OAC medication fill over the course of the follow-up, the primary endpoint, will be summarized and compared between the early intervention and delayed intervention arms. The definition for OAC medication fill will be an OAC medication billing in the pharmacy claims or at least 4 INR tests billed in the laboratory claims (indicative of OAC use that was not billed through the pharmacy claims data). To evaluate whether the comprehensive evaluation and customized multilevel (patient-level and provider-level) educational interventions increases the rate of use of oral anticoagulants at one year post intervention, we will evaluate the odds ratio (i.e. the odds of an average patient in the early intervention group taking OAC at 1 year compared to the odds of an average patient in the delayed intervention group taking OAC at 1 year) using logistic regression to account for the effect of Data Ppartner and adjust for other potential baseline risk factors. ³⁸ We will

present the odds ratio, 95% confidence interval, and p-value to show whether there is a difference in rate of use of OAC at one year post intervention between the early intervention and delayed intervention groups. Similarly, we will analyze the proportion of days covered with an OAC prescription fill over the course of the follow-up. Patients will only be included in this analysis, if they had a prescription fill for apixaban, dabigatran, edoxaban, rivaroxaban, or warfarin.

Event rates for the following secondary outcomes will be summarized by treatment group, as defined by claims data:

- Stroke or TIA
- Ischemic stroke or unknown stroke
- Hemorrhagic stroke
- Hospitalization for any bleeding
- Composite of ischemic or hemorrhagic stroke
- Composite of ischemic stroke, hemorrhagic stroke, and hospitalization for any bleeding

For time-to-event outcomes, Kaplan-Meier cumulative incidence estimates and log-rank test will be utilized. ³⁹ In addition, Cox proportional hazards model with early intervention vs. delayed intervention as main effect will be used to assess the clinical outcomes, after adjusting for baseline risk factors. ⁴⁰ A robust sandwich covariance estimate or a frailty model will be used to account for effect of Data Partner. The hazard ratio, 95% confidence interval and p-value will be presented to summarize the difference in the risk of clinical outcome between early intervention and delayed intervention group. Inhospital death or medically attended death will be collected through claims data. Analyses will be performed using SAS software version 9.4 or higher (SAS Institute, Inc., Cary, NC).

More details on the statistical methods and analyses will be provided in the SAP. The SAP will be finalized prior to study database lock, 12 months after at least 80% of the early intervention mailings. Of note, all patient-level data will be maintained by the Data Partners, so analyses are expected to be conducted via a distributed SAS programming code developed by the coordinating center and results are expected to be returned, by Data Partner, in aggregate to the coordinating center. Analyses will be examined by Data Partner and across Data Partners.

XVII. DISSEMINATION PLAN OVERVIEW

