Among AF patients with guideline indications for OAC for stroke prevention who have not received any OAC dispensing for at least one year, an education intervention at the patient-level and the provider-level will increase the proportion of patients started on OAC for stroke prevention.

IV. STUDY RATIONALE

Preliminary data from three Sentinel Data Partners between 1/1/2006 and 6/30/2015, identified 231,696 patients (1.4%) with at least 2 diagnoses of AF (ICD-9 codes of 427.31 or 427.32) over the study period, among 16.2 million covered lives. Within the 231,696 AF patients, there were 201,882 with a CHA₂DS₂-VASc score of 2 or greater (based on administrative claims data in the Sentinel Distributed Database), which is an American Heart Association (AHA)/American College of Cardiology (ACC) guideline indication for OAC. Over the study period from 2006 through 2015, 52% (n=105,256) patients filled at least one prescription for anticoagulation, meaning that 48% of patients with CHA₂DS₂-VASc score of 2 or greater never had a pharmacy claim submitted for an OAC during the study period. While there may be clinical or health system related reasons for not treating some of these patients, this apparent significant gap of guideline-based adherence is a public health issue of interest. The presented protocol is an opportunity to test the potential for developing and testing a health plan (Data Partner) based education intervention to improve the quality of care.

V. STUDY OBJECTIVES

A. PRIMARY OBJECTIVE

The primary objective is to evaluate the effect of the patient and provider education interventions (versus usual care with delayed provider education intervention) on the proportion of patients with evidence of at least one OAC prescription fill (defined as one OAC dispensing or 4 INR tests) over the course of the follow-up through the date on which at least 80% of eligible study participants have at least 12 months of follow-up time.

B. SECONDARY OBJECTIVE

The secondary objectives are to evaluate the impact on outcomes of the patient and provider education interventions over the course of the follow-up through the date on which at least 80% of eligible study participants have at least 12 months of follow-up time:

- 1. Incident rate of stroke or transient ischemic attack (TIA) hospitalization
- 2. Incident rate of hospitalization for stroke
- 3. Time to first OAC prescription fill
- 4. Proportion of days covered by OAC prescription fills

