- 5. Proportion of patients actively on OAC at 12 months of follow-up
- 6. Incident rate of hospitalization for any bleeding
- 7. All-cause in-hospital mortality rates
- 8. All-cause mortality rates among patients with accurate out-of-hospital mortality data (such as Medicare Advantage patients)
- 9. Health care utilization for AF patients, which would be reported as counts of number of health care utilization events (outpatient visits, days hospitalized, number of emergency department visits, etc.)

C. EXPLORATORY OBJECTIVES

The exploratory objectives are to:

- 1. Evaluate the effect of the early and delayed education interventions on primary and secondary endpoints over the course of the follow-up through the date on which at least 80% of eligible study participants have at least 24 months of follow-up time.
- 2. Explore the CTTI and the FDA supported Sentinel Data Partnership's ability to successfully conduct a pragmatic trial to answer important questions to improve public health.

VI. STUDY DESIGN AND DURATION

The study is a prospective, randomized, and open-label education intervention trial. Patients with AF and a CHA₂DS₂-VASc score of 2 or greater will be randomized in a 1:1 ratio to an early intervention cohort and a delayed intervention cohort within each participating health plan. The definition for OAC medication fill will be an OAC medication dispensing or at least 4 INR tests in the claims data.¹ The claims records of the patients randomized to the early intervention cohort will then be linked to "fresh" (i.e. about 1-4 months old) pharmacy claims data at the time of randomization. Patients without evidence of an OAC medication fill during the 12 months prior to randomization will be included in the patient-level and provider-level early educational intervention (patients randomized to this early intervention with evidence of an OAC medication fill during the 12 months prior to randomization will be excluded from the trial.). In addition to usual care, these patients and their providers² will receive a

¹Not all OAC dispensings are well captured in pharmacy claims, particularly, for warfarin. INR tests are assumed indicative of OAC fills that were not billed through the claims. 4 INR tests or values within a 12-month period will be used as a proxy since that is roughly the number of tests administered in the process of stabilizing dose.

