A schematic diagram below shows the design of the delayed intervention portion of the study:

*All possible person-time will be used to assess participants' outcomes (patients will have different duration of follow-up).

For analysis, treatment status is at time of randomization or corresponding early intervention mailing; for the delayed intervention mailing it is prior to mailing.

VII. STUDY POPULATION

All inclusion and exclusion criteria will be determined by claims data. For entry into the study, the following criteria will be met:

A. INCLUSION CRITERIA

- 1. Two or more diagnoses of AF (ICD-9 and/or ICD-10 codes) at least one day apart and with at least one diagnosis within the last 12 months prior to the last date in the current approved data used for cohort identification
- 2. CHA₂DS₂-VASc score of 2 or greater
- 3. Medical and pharmacy insurance coverage of at least the prior year as identified via administrative claims databases of one of the participating Data Partners as of the date of randomization
- 4. Age 30 years or greater as of the last date in the current approved data used for cohort identification

B. EXCLUSION CRITERIA

- 1. Evidence of OAC medication fill (defined as 1 OAC dispensing or 4 INR tests) during the 12 months prior to randomization (determined at randomization for the early intervention cohort and 12 months post-randomization for the delayed intervention cohort)
- 2. Conditions other than AF that require anticoagulation, including treatment of deep venous thrombosis, pulmonary embolism, or ever having had a mechanical prosthetic heart valve prior to the last date in the current approved data used for cohort identification
- 3. Pregnancy within 6 months of the last date in the current approved data used for cohort identification
- 4. Any known history of intracranial hemorrhage prior to the last date in the current approved data used for cohort identification
- 5. Hospitalization for any bleeding within the last 6 months of the last date in the current approved data used for cohort identification
- 6. Patients with recent P2Y12 antagonist use (i.e. clopidogrel, prasugrel, ticlopidine, or ticagrelor within 90 days of the last date in the current approved data used for cohort identification

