The complete code list for inclusion and exclusion criteria is accessible on the Sentinel website (https://www.sentinelinitiative.org/FDA-catalyst/projects/implementation-randomized-controlled-trial-improve-treatment-oral-anticoagulants-patients).

VIII. INTERVENTIONS

A. PATIENT-LEVEL INTERVENTIONS (EARLY INTERVENTION ARM)

- Letters to patients that (1) explain to the patient that he or she appears to have AF, characterize the risk of stroke, and emphasize that although there may be a medical reason, the patient does not seem to be on an anticoagulant and (2) encourage the patient to discuss this with his or her provider to ask if he or she might benefit from OAC therapy to prevent stroke.
- Written education materials about AF and anticoagulants, including answers to commonly asked questions
- Website with the patient-focused information contained in the letters to patients

B. PROVIDER-LEVEL INTERVENTIONS (EARLY INTERVENTION AND DELAYED INTERVENTION ARM)

- Letters to providers:
 - Early intervention letters to providers that explain this project, the nature of the problem, and identify a list of the provider's patients who have been contacted, as the provider and patient letters will be sent at approximately the same time; describe evidence and guidelines regarding oral anticoagulation
 - Delayed intervention letters to providers that explain this project, the nature of the problem, and identify a list of the provider's patients who are at risk for stroke and have not been treated with an oral anticoagulant; describe evidence and guidelines regarding oral anticoagulation
- Response mailer that gives the provider the opportunity to share the rationale for his or her patient(s) not being on OAC

- Web portal with access to clinical practice guidelines, decision support tools including from professional societies, podcasts, and case studies targeted at improving the appropriate use of OAC for AF
- Information sheet describing top misperceptions of barriers to OAC use
 - 1. Misperception of benefit and risk of aspirin: it is neither safe nor effective
 - 2. Misperception around risk of resuming OAC (months) after bleeding
 - 3. Misperception around risk of OAC regarding patients who fall
 - 4. Opportunities with NOACs for patients who have not tolerated warfarin
 - 5. Concern about lack of an antidote for the NOACs

IX. METHOD OF ASSIGNING PATIENTS TO AN INTERVENTION

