[figure not shown]
Details on the analyses are provided in Section II. Here we describe the data sources for the **modified intention-to-treat** (primary) and **as-randomized** (sensitivity) analyses. Similar to early intervention cohort, the patients in the delayed intervention cohort will be assigned to wave 1 or wave 2 (“pseudo”

³Not all OAC dispensings are captured in pharmacy claims, particularly, for warfarin due to some patients paying for medication out of pocket. INR tests are assumed indicative of OAC fills that were not billed through the claims. Four INR tests or values within a 12-month period will be used as a proxy since that is roughly the number of tests administered in the process of stabilizing dose.

wave assignments) depending on the difficulty in identifying the patient's provider (the intent is to handle them the same way as was done for the early intervention arm, for the modified intention-to-treat analysis). The follow-up for the delayed intervention patients will start on the date the wave 1 or 2 mailings took place for a given Data Partner's early intervention cohort. For both early and delayed intervention cohorts, any patients who die, are disenrolled, or get started on OAC between the randomization and early intervention mailing will be excluded from the analysis at each Data Partner. For both the early and delayed arms, exclusion criteria that are based on member medical history were assessed at the time of randomization. For the early intervention cohort, enrollment and treatment status were assessed at randomization for all and re-assessed at the wave 2 time point at some of the sites (this was at site discretion, in response to the lag between wave 1 and 2 mailings). The enrollment and treatment status of the delayed intervention cohort will be examined for eligibility at the same time point as the early intervention patients, meaning at the time of mailing per Data Partner, via the locked data (using the wave 1 and 2 dates).

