Where $T = (p_{12}, p_{13}, \dots, p_{1k})'$, $p_{1k} = \Pr(\text{category } k \mid \text{early intervention})$, $k \in \{2, 3, \dots, k\}$,

$C = (p_{22}, p_{23}, \dots, p_{2k})'$, $p_{2k} = \Pr(\text{category } k \mid \text{delayed intervention})$, $k \in \{2, 3, \dots, k\}$,

S is a $(k - 1) \times (k - 1)$ covariance matrix define as:

$$S = [S_{kl}] = \begin{cases} \frac{[p_{1k}(1 - p_{1k}) + p_{2k}(1 - p_{2k})]}{2}, & k = l \\ \frac{[p_{1k}p_{1l} + p_{2k}p_{2l}]}{2}, & k \neq l \end{cases}$$

Aggregate standardized mean differences will be calculated based on aggregated frequencies, mean, and standard deviations.

Each Data Partner will run the SAS program(s) distributed by HPHCI, developed with the statistical team at Duke, to generate a summary table for their cohort of patients shown in example Tables 1 and 1S in Appendix A (there will be one for each Data Partner) and return the summary table to HPHCI. The same summary table will be generated for entire study population by HPHCI, as shown in Tables 1 and 1S in Appendix A.

As part of the provider intervention materials, providers had the opportunity to respond and provide an explanation for why their patients were not being treated with OAC. The data collected from these responses will be aggregated by rationale for non-treatment and reported as counts (percentages) by the coordinating center.

C. PRIMARY ENDPOINT DATA ANALYSES

The proportion of patients with evidence of at least one OAC medication fill over the course of the follow-up (through the date on which at least 80% of eligible study participants have at least 12 months of follow-up time) is the primary endpoint. The definition for OAC medication fill will be an OAC medication billing in the outpatient pharmacy claims, at least 4 INR tests or results in the laboratory claims (indicative of OAC use that was not billed through the pharmacy claims data), or a single procedure code that indicates use of anticoagulation. The primary endpoint will be summarized and compared between the early intervention and delayed intervention arms. Both unadjusted and adjusted

(based on available baseline risk factors) analyses will be conducted for the difference in the primary endpoint between the early intervention and delayed intervention arms using the data shown in Tables 2a-c. The adjusted analysis will be considered the primary analysis.

1. Adjusted Analysis Model

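### The baseline OAC exclusion reuses the endpoint's 4-INR threshold, so unbilled warfarin users with 1-3 INR tests in the look-back year enter as untreated and can later be scored as starters

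*Protocol*

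**What the plan says.** - **One definition, two uses.** Protocol VI states it: "The definition for OAC medication fill will be an OAC medication dispensing or at least 4 INR tests in the claims data". Exclusion 1 (Protocol VII.B) uses it to remove existing users: "Evidence of OAC medication fill (defined as 1 OAC dispensing or 4 INR tests) during the 12 months prior to randomization". The primary objective (Protocol V.A) uses it to count starts: "evidence of at least one OAC prescription fill (defined as one OAC dispensing or 4 INR tests".
- **Why INR tests count.** Protocol VI, footnote 1: "INR tests are assumed indicative of OAC fills that were not billed through the claims". SAP I.F, footnote 3 adds that dispensings are missed, above all for warfarin, "due to some patients paying for medication out of pocket".
- **Why four.** Both footnotes give the same single reason: four tests or values in 12 months are "used as a proxy since that is roughly the number of tests administered in the process of stabilizing dose".
- **Endpoint routes in the SAP.** SAP II.C accepts a billed dispensing, "at least 4 INR tests or results in the laboratory claims", or one procedure code that indicates anticoagulation. The exclusion as stated does not mention the third route.
- **What is to be estimated.** Protocol VI describes the comparison as concerning patients who were not on an OAC in the year before randomization and were then started.
- **What is planned nearby.** Table A (SAP Appendix A) has no INR covariate. The as-randomized sensitivity analysis (SAP II) applies a 365-day washout without a lower INR threshold. Tables 2a and 3 split endpoint events by route, but not by baseline INR testing.

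**The concern.** The two uses need different things from the rule. For the endpoint, a strict threshold is sensible because it guards against calling a stray INR test a start. For the exclusion, the task is to find people already on warfarin, whose dose may be stable. A count typical of dose-finding is then too demanding: unbilled users with 1-3 tests pass. The plan gives no separate reason for using 4 in this role.

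An existing user scored as a starter falls outside the stated comparison. The scored event is existing treatment becoming visible in claims, not new treatment. At stake are the meaning of the initiation proportion, its absolute level and the size of the effect. As the tables stand, a reader could not separate new starts from existing use.

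**Working it through.** **1. The plan's own figure.** Inputs from Protocol XIV.A.1: 33% vs 38%, two-sided 0.05, continuity-corrected chi-square, 30% attrition. The two-proportion formula with continuity correction gives 1963, 2418 and 3401 per arm for 90%, 95% and 99% power. Dividing by 0.7 gives 2805, 3455 and 4859, exactly as tabulated. (The protocol labels that table as unadjusted for dropouts, but the figures reproduce only after the division.) With about 80,000 patients randomized 1:1, 40,000 × 0.7 = 28,000 are evaluable per arm.

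**2. Who passes the exclusion and is later scored, by INR alone within 365 days** (the window in Table 2a). The documents give no testing intervals, so those below are assumed.

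*Regular testing every d days, random phase.* Below 365/4 ≈ 91 days there are at least 4 tests a year and the user is excluded. Above 365/3 ≈ 122 days there are never 4. In between, let f = 365/d − 3. Then P(3 at baseline) = 1 − f, and P(3 at baseline, then 4) = min(f, 1 − f).

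| d (days) | f | Passes, then scored | Scored, given passed |
|---|---|---|---|
| 95 | 0.842 | 16% | 100% |
| 100 | 0.650 | 35% | 100% |
| 104 | 0.510 | 49% | 100% |
| 110 | 0.318 | 32% | 0.318/0.682 = 47% |
| 115 | 0.174 | 17% | 0.174/0.826 = 21% |
| over 122 | n/a | 0% | 0% |

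*Irregular testing (independent Poisson counts).* At 2, 3 and 4 tests a year, the chance of at least 4 in the next 12 months is 14%, 35% and 57%. The chance of passing and then being scored is 12%, 23% and 25%.

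Longer follow-up could raise these figures. Protocol XV item 2 counts INRs over the study period, and Protocol VI uses all available person-time. At 18 months the joint Poisson figures become 30%, 43% and 37%. A later billed fill or the procedure code would add an unknown amount.

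**3. Effect on the comparison.** Let s be the share of analysed patients who are existing users and q the share of them scored, equal in both arms.

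- Observed rate = (1 − s) × true rate + s × q
- Observed difference = (1 − s) × 5.0 points; q cancels

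| s (assumed) | Difference |
|---|---|
| 2% | 0.98 × 5.0 = 4.9 |
| 5% | 0.95 × 5.0 = 4.75 |
| 10% | 0.90 × 5.0 = 4.5 |

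At 28,000 per arm, power stays above 99.9% in all three cases. With no true effect the observed difference is (1 − s) × 0 = 0.

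**4. Effect on the delayed-arm rate.** It rises only if q exceeds the true rate. At s = 5%, 0.95 × 33% = 31.35%. Adding 5% × q for q = 14%, 35% and 57% gives 32.1%, 33.1% and 34.2%. The first is a fall.

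**The case against.** **The effect is small and visible.** The dilution is 0.1 to 0.5 of 5 points, power is untouched, and Tables 2a and 3 already show how many patients met the endpoint through INR tests. This stands as to size. It does not remove the point, because a split by route cannot tell an INR-route starter who was untreated from one who was already treated, and an existing user with a later billed fill appears under dispensings.

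**Few such users may exist.** The documents do not say that established users have fewer than 4 tests a year, nor how many pay out of pocket. This also stands: every share and interval above is an assumption. Regular testers at 1-2 a year do not reach 4 in 365 days. One additional test over the baseline year is enough only for a patient who had 3.

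**Stronger readings that the documents do not support:**

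- *Upward bias.* Only the early arm is sent a letter saying "the patient does not seem to be on an anticoagulant" (Protocol VIII.A). A reader might infer that this prompts existing users to have the next fill or test billed, producing a false effect. The letter asks the patient to discuss treatment with the provider. Nothing in the documents concerns billing, and the endpoint rule is the same in both arms.
- *An inflated initiation rate.* This does not follow either: step 4 shows that the rate can fall. The planning rate of 33% came from a cohort with similar criteria (Protocol XIV.A.1), so it may already include such users.

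**Conclusion.** The point holds as a misclassification at entry. The plan applies to existing users a threshold that it justifies only for new starters, acknowledges that unbilled warfarin users exist, and pre-specifies nothing that uses a baseline count of 1-3 INRs. Such users can be scored as starts; whether many will be is unknown.

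The expected consequence is modest dilution (5.0 points to 4.9, 4.75 or 4.5 for assumed shares of 2%, 5% or 10%) and a less clear meaning of having been started on an OAC. This rests on balance by randomization and equal scoring in both arms. It does not threaten power and gives no ground to expect a false positive. The direction of any shift in the absolute rate is undetermined.

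**What to change.** Keep 4 INRs for the endpoint and leave the main analysis population unchanged. Before the SAP is finalized:

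1. Pre-specify a repeat of the primary mITT model restricted, in both arms, to patients with no INR test in the 12 months before randomization.
2. In Table 2a, split the starters by arm and by baseline INR tests, 0 vs 1-3.
3. Add baseline INR testing (0 vs 1-3) to Table A as a prognostic covariate. This is for precision only and does not remove mis-scored starts.

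Take the count from the same data source and look-back in both arms. SAP I.D names only pharmacy and enrollment data as freshly linked and describes the routine data as several months old.

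The cost is SAP wording and a few program lines. The variable precedes randomization, so the restriction preserves the randomized comparison, and applying exclusion 1 already requires INR tests to be counted. The restricted analysis drops some truly untreated patients who had an INR test for another reason, so it is slightly less precise. It also cannot find users whose INR tests never reach the claims.
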